6.15 Tertiary Aim Study Procedures Schedule

Tertiary Aim	Visit 16	Visit 17	Visit 18	Visit 19	Visit 20	Visit 21	Visit 22	Visit 23
Procedures	Week 10	Week 16	Week 20	Week 24	Week 28	Week 32	Week 36	Week 38
Phone Call Follow up	I	B	B	B	B	B	B	
Seizure Diary/Adverse Events	I	B	B	B	B	B	B	
Medication Review	I	B	B	B	B	B	B	
TICS/KOKMEN	I	B	B	B	B	B	B	
Antibody Testing (VGKC, LGI1, CASPR2)						I		P
Standard of Care visit at Mayo Clinic						I		P

TICS=Telephone interview for cognitive status

Tertiary Aim	Visit 24	Visit 25	Visit 26	Visit 27	Visit 28	Visit 29	Visit 30	Visit 31
Procedures	Week 40	Week 44	Week 48	Week 52	Week 56	Week 58	Week 60	Week 64
Phone Call Follow up	B	B	B	B	B		P	
Seizure Diary/Adverse Events	B	B	B	B	B		P	
Medication Review	B	B	B	B	B		P	
TICS/KOKMEN	B	B	B	B	B		P	
Antibody Testing (VGKC, LGI1, CASPR2)						I		P
Standard of Care visit at Mayo Clinic						I		P

7 Statistical Plan

7.1 Statistical Methods

Dr. [REDACTED], senior statistician and Professor of Biostatistics, will be responsible for analyzing study data. The treatment (IVIg or placebo) will be unblinded at the 6 week follow up.

Randomized Placebo Controlled Trial:

The study will include 30 patients (15 per arm). Data collected will be summarized using descriptive statistics such as mean, standard deviation, median, minimum and maximum for continuous variables and using frequencies and percentages for categorical variables (see Study Endpoints). Primary outcome, which is binary variable, i.e. proportion of patients responding to treatment (yes, no) will be estimated along with 95% exact binomial confidence intervals for each arm of the respective study. These proportions will then be compared using Fisher's exact test within the study. Continuous outcomes of interest will be compared using two sample t-test or Wilcoxon rank sum test as appropriate.

Multiplicity

Due to smaller sample sizes, no adjustment for multiple comparisons is done.

Power/Sample Size

Sample size and power calculations for various scenarios using Nquery advisor software version 7.0 are provided below.

VGKC complex antibody positive

Based on preliminary data, assuming 70% responders on IVIG vs. 10% on Placebo, a total sample size of 30 (i.e.15 per group) will have 89% power at an alpha level of 5% using Fisher's exact test.

Dropouts

If we assume a maximum dropout rate of 20%, we would still maintain >80% power. In an event if the dropout rate exceeds anticipated rate, we would still have 82% power to detect hypothesized difference (70% versus 10%) with as few as 12 patients per group.

Effect of patient enrolment on power analysis in Randomized Placebo Controlled Trial

Group 1: Assuming the rate of positive response to IVIG and placebo is 70% and 10%, respectively:

Two group Fisher's-exact test of equal proportions (odds ratio = 1) (equal n's)

	1	2	3	4
Power (%)	82	89	94	97
n per group	12	15	17	19

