7.2 Endpoints

Primary endpoints*

- 1) Change in seizure frequency

The definition of a “responder” is a patient with a $\geq 50\%$ reduction in seizure frequency.

Secondary endpoints

Clinical factors predictive of immunotherapy response.

The following clinical factors will be analyzed with respect to prediction/correlation with favorable outcome.

- 1) Interval from symptom onset to immunotherapy treatment
- 2) Type of onset
- 2) Clinical course
- 3) Seizure type and frequency
- 4) EEG abnormalities
- 5) Presence of other neurological symptoms or signs (tremor, headache, myoclonus)
- 6) CSF findings (White cell count; protein)
- 7) Neural autoantibody type (LGI1, CASPR2, other) and titer (blood draws will be performed at baseline, 6 weeks and 12 weeks (for placebo group only)
- 8) Change in The Repeatable Battery for the Assessment of Neuropsychological Status (RBANS) scale scores

Tertiary endpoints

For the 1 year follow up “observational study”

- “Responder” patients from Trial will be randomly assigned to 2 clinical groups:
 - Immunotherapy (as per physician/insurance approval): mycophenolate mofetil 2000mg daily or azathioprine 2mg/kg +/- IVIG taper or IVMP taper
 - No immunotherapy
- Subjects will be followed for relapse for a total of 12 months (see study schedule of events).
- Patients will keep a daily seizure diary and record any adverse events while on immunotherapy.
- The study coordinator will call patients every month review seizure history and adverse events.
- Patients will be seen at 6 months and 12 months as part of standard clinical care-neurological examination will be recorded.
- Relapse will be defined as $\geq 20\%$ increase in seizure frequency compared with post IVIG frequency.
- Cognition will be assessed by the study coordinator who will perform Telephone Interview for Cognitive Status and the KOKMEN at each monthly call.
- If relapse occurs, the patient will be seen at the clinic. Patients on no therapy will be started on immunotherapy, those on therapy will have treatment adjusted as per current standard clinical care.

8 Safety and Adverse Events

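### Fisher's exact test at 15 per arm uses at most 1.8% of its nominal 5%, and no interval is planned for the IVIG minus placebo difference: a cheap improvement to section 7.1, not an error in it

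*Combined protocol and SAP*

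**What the plan says.** The primary outcome is binary: response means a reduction of at least 50% in seizure frequency (section 7.2). For this outcome, section 7.1 and the Study Summary plan two things.

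- **Estimation:** the responder proportion "will be estimated along with 95% exact binomial confidence intervals for each arm of the respective study".
- **Comparison:** "These proportions will then be compared using Fisher's exact test within the study".

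No section plans a risk difference, risk ratio or odds ratio with a confidence interval for the primary outcome. The odds ratio of 1 in the power table is only the null hypothesis.

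On power, 7.1 states that "a total sample size of 30 (i.e.15 per group) will have 89% power at an alpha level of 5% using Fisher's exact test", under 70% responders on IVIG and 10% on placebo. For dropout it adds that "we would still have 82% power to detect hypothesized difference (70% versus 10%) with as few as 12 patients per group". It does not say whether the test is one-sided or two-sided.

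**The concern.** Randomisation 1:1 fixes the number of patients in each arm but not the total number of responders. Fisher's test conditions on both. With so few patients the conditional p-value takes few distinct values, so the true type I error lies well below the nominal 5%. The unused error rate costs power, and this trial has little to spare: 30 patients, with a 20% dropout allowance.

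The second issue concerns the result itself. Sections 3.2 and 5.2 ask about efficacy of IVIG relative to placebo, and the background (1.1) explains that insurers' refusals to cover IVIG motivate the trial. The size of the difference and its precision are therefore the main result. A p-value and two separate per-arm intervals do not give that precision.

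**Working it through.** **Inputs** (section 7.1): 15 per arm; response 70% v 10%; alpha 5%; Fisher's exact test; dropout case 12 per arm. Two-sidedness is an assumption, tested in step 1.

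**Formulas.** For each pair (i, j) of responder counts, let R(i, j) = 1 if the test rejects and 0 otherwise. With b(k; n, p) the binomial probability:

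- Power = Σ R(i, j) · b(i; n, p₁) · b(j; n, p₀)
- True size = the maximum over a common rate p of Σ R(i, j) · b(i; n, p) · b(j; n, p), on a grid from 0.001 to 0.999

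Boschloo's test orders the tables by their Fisher p-value. Its own p-value is the maximum, over the common rate, of the probability of a table at least that extreme. At 15 per arm all 16 × 16 tables were enumerated.

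**Step 1: reproduce the plan's power (Fisher, two-sided 5%, 70% v 10%).**

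| n per arm | Plan | Recomputed |
|---|---|---|
| 12 | 82% | 82.6% |
| 15 | 89% | 89.4% |
| 17 | 94% | 94.8% |
| 19 | 97% | 97.5% |

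All four reproduce. A one-sided 5% test at 15 per arm would give 95.0%, so the plan's test is in effect two-sided 5% (one-sided 2.5% gives the same 89.4%).

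**Step 2: true size at a nominal two-sided 5%.**

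| n per arm | Fisher, maximum | Boschloo, maximum |
|---|---|---|
| 15 | 1.77% (common rate near 0.24) | 4.33% |
| 12 | 2.28% | 4.49% |

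At a common rate of 10%, the assumed placebo rate, Fisher's size at 15 per arm is 0.55%. Every table that Fisher rejects is also rejected by Boschloo.

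**Step 3: power under both tests.**

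| Scenario | Fisher | Boschloo | Gain (points) |
|---|---|---|---|
| 70% v 10%, 15 per arm | 89.4% | 95.0% | 5.6 |
| 70% v 10%, 12 per arm | 82.6% | 89.5% | 6.9 |
| 70% v 20%, 15 per arm | 68.0% | 80.7% | 12.7 |
| 60% v 10%, 15 per arm | 73.9% | 84.5% | 10.6 |
| 80% v 10%, 15 per arm | 97.5% | 99.1% | 1.6 |

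At 70% v 10%, Boschloo with 15 per arm (95.0%) matches Fisher with 17 (94.8%). Boschloo with 12 per arm (89.5%) matches Fisher with 15 (89.4%).

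**Step 4: which results change.** Take 8/15 v 2/15, with 10 responders among 30. The upper-tail probability is [C(15,8)·C(15,2) + C(15,9)·C(15,1) + C(15,10)] / C(30,10) = (675,675 + 75,075 + 3,003) / 30,045,015 = 0.02509. Doubling it, since the arms are equal, gives Fisher p = 0.0502.

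| IVIG v placebo responders (of 15) | Fisher p | Boschloo p |
|---|---|---|
| 8 v 2 | 0.0502 | 0.023 |
| 9 v 3 | 0.060 | 0.030 |
| 6 v 1 | 0.080 | 0.043 |
| 4 v 0 | 0.0996 | 0.043 |

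**Step 5: what an interval for the difference would show.** At 11/15 v 2/15 the difference is (11 − 2)/15 = 60 points, with a 95% interval of about 25 to 78 (Newcombe) or 26 to 81 (score). The planned per-arm intervals there are 45% to 92% and 2% to 40%; neither states the precision of the 60-point difference.

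**The case against.** The strongest reply is that nothing in the plan is wrong. Fisher's test is prespecified, protects the type I error, and is the test for which power was computed. By that calculation power stays above 80% even at 12 per arm. All of this stands, and the gain is measured against a test the plan never promised.

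The argument about margins is also open. Under a randomisation model with a sharp null, the total number of responders is fixed and Fisher is the natural test. Patients come from one centre's laboratory, clinics and referrals (4.3), so that model is defensible. This makes the choice of test a matter of efficiency and preference.

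A reader might infer a general six-point loss. The documents do not support that: section 4.3 anticipates 80–100% response, and at 80% v 10% the gain is 1.6 points. It is larger if IVIG response is lower or placebo response higher than planned. Section 8.5 makes the latter plausible by noting that some patients recover spontaneously.

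A reader might also infer that clearly positive results would be declared negative. The tables that change are borderline: at 8/15 v 2/15 the Newcombe interval for the difference is about 6 to 64 points. The change would also make 4/15 v 0/15 significant.

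On the interval, both proportions are planned, so the point difference is immediate and a reader could compute its interval. That makes the gap small to repair, but the primary effect measure should still be prespecified.

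**Conclusion.** The point holds as a cheap improvement to section 7.1. At 15 per arm, two-sided Fisher has a true size of at most 1.8%. Boschloo stays at or below 5%, loses no rejection, and adds 5.6 points of power at the planned rates, worth about two patients per arm. The missing between-arm interval is the more important half, because it concerns the quantity in the primary aim.

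Three stronger readings fail. Type I error is not inflated. The 89% is not miscalculated. Boschloo does not use the full 5%, since its maximum size here is 4.3%; it is only less conservative.

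The figures assume a two-sided 5% test, which 7.1 does not state but its power figures imply, and two independent binomial samples. The size of the gain depends on the sample size and the two response rates.

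**What to change.** In section 7.1, and in the matching text of the Study Summary:

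1. Prespecify the IVIG minus placebo risk difference with a 95% interval (Miettinen–Nurminen score or exact unconditional), and keep the per-arm intervals.
2. Make Boschloo's exact test, two-sided at 5%, the primary comparison, with Fisher's test as a sensitivity analysis.
3. State that the test is two-sided.
4. Keep n = 30. Either keep 89% as a conservative power figure or restate it as 95%.
5. Say that the test, not the interval, decides significance, because the two can disagree near the boundary. At 8/15 v 2/15 the Newcombe interval excludes zero while Fisher gives 0.0502.

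The uncorrected Pearson chi-square is not a clean substitute: its maximum size at 15 per arm is 5.5%.

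**Timing.** Sections 6.5 and 7.1 unblind each patient at week 6, so results by arm become known one patient at a time. Make and date the amendment before any outcome is tabulated by arm. If patients have already been unblinded at week 6, keep Fisher as primary and add only the interval; moving then to a test that rejects more tables could look data-driven.

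**Cost.** A few lines of text and standard software, with no extra patients, visits or data. The downside is that some statisticians prefer the conditional test, which the sensitivity analysis answers.

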GAMUNEX-C is made from large pools of human plasma by a combination of cold ethanol fractionation, caprylate precipitation and filtration, and anion-exchange chromatography. Isotonicity is achieved by the addition of glycine. GAMUNEX-C is incubated in the final container (at the low pH of 4.0–4.3). The product is intended for intravenous administration and may be administered subcutaneously in treatment of PI.

The capacity of the manufacturing process to remove and/or inactivate enveloped and non-enveloped viruses has been validated by laboratory spiking studies on a scaled down process model, using the following enveloped and non-enveloped viruses: human immunodeficiency virus, type I (HIV-1) as the relevant virus for HIV-1 and HIV-2; bovine viral diarrhea virus (BVDV) as a model for hepatitis C virus; pseudorabies virus (PRV) as a model for large DNA viruses (e.g., herpes viruses); Reovirus type 3 (Reo) as a model for non-enveloped viruses and for its resistance to physical and chemical inactivation; hepatitis A virus (HAV) as relevant non-enveloped virus, and porcine parvovirus (PPV) as a model for human parvovirus B19.

Overall virus reduction was calculated only from steps that were mechanistically independent from each other and truly additive. In addition, each step was verified to provide robust virus reduction across the production range for key operating parameters.

2 Study Objectives

This study evaluates the utility of IVIG in the evaluation and management of patients with suspected autoimmune epilepsy associated with voltage gated potassium channel complex autoantibodies (VGKC Ab).

Primary Aim

- To assess in a blinded randomized controlled fashion, whether 5 weeks of IVIG can reduce or stop seizures in patients with VGKC Ab associated autoimmune epilepsy.
- To evaluate the safety and tolerability of IVIG in VGKC Ab associated autoimmune epilepsy.

Secondary Aim

- To investigate clinical factors predictive of immunotherapy response.
- To assess whether IVIG improves cognitive performance [$\geq 20\%$ on Repeatable Battery for the Assessment of Neuropsychological Status (RBANS)] in patients undergoing IVIG therapy for VGKC Ab associated epilepsy.

Tertiary Aim

To perform a 1 year observational follow up to investigate factors (including maintenance immunotherapy vs. no therapy) influencing relapse rate after positive IVIG response

[figure not shown]

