All patients will receive phone calls from the clinical research coordinator at 2 weeks, 4 weeks to assess patient reported side effects and record seizure diary information. The placebo group that will receive IVIG in an open label fashion, will also receive phone calls every week (weeks 7-11) to assess patient reported side effects and record seizure diary information. Any side effects or increase in seizure frequency from previous baseline will be reported to the principal investigator or designee to determine if any action should be taken or if un-blinding is required. Patients will also be given 24 hour emergency contact information for the study team to carry with them at all times.

Treatment location:

First 4 infusions will be given at Mayo Clinic using Mayo's standard operating procedures for infusion administration (see appendix 1). This will allow study personnel to closely evaluate the patient and give the home care network time to set the home treatment.

Home infusions:

The 4 IVIG infusions for those 15 initial placebo group patients will be given at the patient's home or clinic near their home. These infusions will be given per Option Care's standard operating procedure (see appendix 2)

In this study we are going to utilize the home care network of Option Care nationwide. Therefore one of the inclusion criteria is that the home treatment network is available where the patient lives.

Our secondary aim firstly investigates clinical factors predictive of IVIG response. These will include antibody type (LGI1, CASPR2, other) and titer. Thus blood draws will be performed at baseline, 6 weeks and 12 weeks (for placebo only). Secondly, we will assess for improvements in cognitive performance as measured by the KOKMEN¹⁷ and the Repeatable Battery for the Assessment of Neuropsychological Status (RBANS).²⁰

Our tertiary aim, a clinical observational study, investigates factors influencing relapse rate after a positive IVIG response. "Responders" from AIM 1 will be randomly assigned in open label fashion by the treating physician to 2 clinical observational groups:

- Immunotherapy (as per physician/insurance approval): mycophenolate mofetil 2000mg daily or azathioprine 2mg/kg +/- IVIG taper or IVMP taper
- No immunotherapy

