3.4 Secondary Study Endpoints

Improvement of 20% or more in cognitive function measured by Repeatable Battery for the Assessment of Neuropsychological Status (RBANS)

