6.1 Visit 1 (Screening)

The following will occur at this visit and last up to 4 hours

- Review of medical history
- Review of past and current medication history
- Vital signs (blood pressure, temperature, heart rate, breathing rates, height and weight)
- Neurologic examination
- Undergo memory and cognitive function assessments (RBANS/ KOKMEN Neuropsych testing)
- Review seizure diary
- Confirmation of stable dose of antiepileptic medications

After the assessments are complete and if the subject still meets all study inclusion criteria blood will be drawn for testing. The amount of blood drawn will be approximately 6 tablespoons or 90mL.

This blood test will look at the following:

- kidney and liver function
- Blood sugar and electrolytes

- IgA immunoglobulins
- Antibody testing
- A pregnancy test if you are a female and able to become pregnant
- Blood for repository for future testing

6.2 Visit 2 & 3; Week-1 Day 1 and Day 2

Mayo Clinic Infusions

Within a few days after the subjects initial evaluation they will receive the first two infusions at the Mayo Clinic Infusion Center. The first infusion (0.5g/kg) drug or placebo will be followed by the second infusion (1g/kg) being given the very next day.

The IVIG infusion is given over approximately 6-8 hours depending on the dose and rate of the infusion. Prior to the infusion the subject will have an intravenous catheter (IV) placed in the subjects arm which will be removed after each infusion is completed.

The subject will be given IV fluids (500 mls of normal saline) before and after the infusion of 1g/kg. The subject will be given acetaminophen (Tylenol) (to prevent headache) and Benadryl (to prevent allergic reaction) before all infusions. Before, during and after the infusions, the subject's vital signs will be monitored.

6.3 Visit 4 & 6; Weeks 2 & 4

Phone Calls

The subject will receive a phone call from the study coordinator at week-2 and again at week-4. During these phone calls, the study coordinator will review the subjects seizure history, medications changes (started any new or stopped any medication), or had any adverse events (side effects, illness, and/or hospitalizations).

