6.4 Visit 5 & Visit 7; Week-3 and Week-5

Mayo Clinic Infusion Center

Week-3 infusion (0.6g/kg drug or placebo) will be given 2 weeks following the 2nd infusion. Week-5 (0.6g/kg drug or placebo) infusion will be given 2 weeks after the 3rd infusion (total of 5 weeks).

6.5 Visit 8; Week 6

Mayo Clinic Examination and Unblinding.

During this visit, patients will be seen in clinic. All required assessments will be documented and signed.

- Review current medication history
- Vital signs (blood pressure, temperature, heart rate, breathing rates, and weight)
- Neurological Examination
- Undergo memory and cognitive function assessments (RBANS/KOKMEN- Neuropsych testing)
- Blood draw to check antibody levels.
- Review Seizure Diary

Then, the study physician and the subject will be unblinded.

If the study subject received placebo, they will be given IVIG in an open label fashion through Option Care Home Infusion service using the same dose and schedule as used for the first portion of this study. The last 4 IVIG infusions for those 15 patients, who received placebo for the first 4 treatments, will be given at the patient's home or clinic near their home. These infusions will be given per Option Care's standard operating procedure. In this study we are going to utilize the home care network of Option Care nationwide. Therefore one of the inclusion criteria is that the home treatment network is available where the patient lives.

If the study subject received IVIG, this will be their Research clinic visit, and they will NOT receive any more infusions for the study, they will only receive the phone calls for long term follow up and proceed to VISIT 16, 26 of the tertiary aim.

6.6 Visit 9 & 10; Week 7: Day 1/Day 2

Option Care Home Infusion

Within a 7-10 days after the subjects Week6 evaluation they will receive the first two infusions through Option Care. The first infusion (0.5mg/kg) IVIG will be followed by the second infusion (1g/kg) being given the very next day.

The IVIG infusion is given over approximately 6-8 hours depending on the dose and rate of the infusion. Prior to the infusion the subject will have an intravenous catheter (IV) placed in the subjects arm which will be removed after each infusion is completed.

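### The cognitive endpoint takes two forms (20% RBANS improvement, RBANS change score), the plan does not say which is compared between arms, and neither adjusts for the baseline RBANS already collected

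*Combined protocol and SAP*

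**What the plan says.** Cognition is part of the secondary aim. Section 2 states the aim as "To assess whether IVIG improves cognitive performance" and attaches a threshold of at least 20% on RBANS. Section 3.4 has a single endpoint with the same threshold: "Improvement of 20% or more in cognitive function measured by Repeatable Battery for the Assessment of Neuropsychological Status (RBANS". Section 7.2 lists, as item 8 of the secondary endpoints, "Change in The Repeatable Battery for the Assessment of Neuropsychological Status (RBANS) scale scores", with no threshold. The sentence governing that list is "The following clinical factors will be analyzed with respect to prediction/correlation with favorable outcome".

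On method, section 7.1 assigns Fisher's exact test to the primary responder outcome. For continuous outcomes it says only: "Continuous outcomes of interest will be compared using two sample t-test or Wilcoxon rank sum test as appropriate". No test is named for the 20% RBANS proportion, and no baseline-adjusted model appears.

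RBANS is scheduled at screening (section 6.1: "Undergo memory and cognitive function assessments (RBANS/ KOKMEN Neuropsych testing"), at week 6 (section 6.5: "Undergo memory and cognitive function assessments (RBANS/KOKMEN- Neuropsych testing") and at week 12 (section 6.9). The table in section 6.14 marks baseline and week 6 for both arms and week 12 for the placebo-first arm only. Treatment is unblinded at the week-6 visit, after the assessments.

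**The concern.** A 20% threshold and a change score are different endpoints, with different tests and very different power. Section 7.1 makes no multiplicity adjustment. If the form is settled only after unblinding, a reader cannot tell a planned cognitive result from a selected one.

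Both forms use the baseline score, one as a denominator and the other by subtraction, but neither adjusts for it. With 30 patients and RBANS already taken in both arms before treatment, an adjusted analysis is available at almost no cost. At stake is the precision of the only endpoint listed in section 3.4.

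Two details are also open. The documents do not say which RBANS score is meant (a total or an index score), or what the 20% is a percentage of.

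**Working it through.** **Calibration on the plan's own figure.** Exact enumeration of the two-sided Fisher test at 5%, 70% v 10% responders:

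| n per arm | plan (7.1) | recomputed |
|---|---|---|
| 12 | 82% | 82.6% |
| 15 | 89% | 89.4% |
| 17 | 94% | 94.8% |
| 19 | 97% | 97.5% |

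The plan's figures reproduce. It gives no power or precision figure for RBANS.

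**Inputs.** From section 7.1: n = 15 per arm, alpha 5% (taken as two-sided, which reproduces the table above), and 12 per arm as the 20% dropout case. Assumed, because the documents give none: RBANS SD 15 at both visits, effect 12 points (0.8 SD), correlation r between baseline and week 6 of 0.5 / 0.7 / 0.8, baseline mean 85, and 20% taken relative to the patient's own baseline score.

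**Step 1: variance per patient.**
- Change score: 2(1 − r) × SD², with 2n − 2 = 28 df.
- ANCOVA: (1 − r²) × SD² × [1 + 1/(2n − 4)], with 2n − 3 = 27 df. The bracket is the expected cost of chance baseline imbalance, 27/26 at n = 15.
- Ratio, ANCOVA to change: (1 + r)/2 × 27/26 = 0.78 / 0.88 / 0.93.
- Per-arm n at which a change-score analysis has the same variance: 15 ÷ ratio = 19.3 / 17.0 / 16.0, about 19 / 17 / 16.

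**Step 2: precision and power (noncentral t).** The 95% CI half-width is t × √(variance × 2/n).

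| r | ANCOVA half-width | change half-width | ANCOVA power | change power |
|---|---|---|---|---|
| 0.5 | 9.9 | 11.2 | 67% | 56% |
| 0.7 | 8.2 | 8.7 | 83% | 78% |
| 0.8 | 6.9 | 7.1 | 93% | 92% |

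At 12 per arm the powers are 56 / 72 / 86% v 47 / 68 / 84%. With SD 10, 15 or 20 at the same 12 points and 15 per arm, the gain runs from 0 to about 11 percentage points.

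**Step 3: where the gain ends.** The ratio reaches 1 when r = 2 × 26/27 − 1 = 0.926 at 15 per arm. At 12 per arm the bracket is 21/20, so r = 2 × 20/21 − 1 = 0.905. At r = 0.9 the two powers are equal to rounding (99.7% each at 15 per arm).

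**Step 4: if the 20% proportion is what is tested.** A patient qualifies when week 6 ≥ 1.2 × baseline. The quantity week 6 − 1.2 × baseline has mean 85 + effect − 102 = effect − 17, and SD 15 × √(2.44 − 2.4r) = 16.7 / 13.1 / 10.8. Then exact Fisher at 15 per arm:

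| r | 12 points: IVIG v placebo | power | 17 points: IVIG v placebo | power |
|---|---|---|---|---|
| 0.5 | 38% v 15% | 16% | 50% v 15% | 36% |
| 0.7 | 35% v 10% | 24% | 50% v 10% | 55% |
| 0.8 | 32% v 6% | 30% | 50% v 6% | 70% |

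ANCOVA at 17 points has 92 / 98 / 100%. If both arms also gain 5 points, the 20% cut gives 18 / 29 / 42% at 12 points. With SD 10, 15 or 20, its power at 12 points runs over 10–32% with no placebo change and 10–75% with the 5-point gain.

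**Step 5: time point.** Week 6 is the only scheduled post-baseline RBANS common to both arms, and it precedes unblinding. The week-12 value exists only for the placebo-first arm, after open-label IVIG. Week 6 is therefore the only randomised, blinded comparison, although no endpoint text names it.

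**The case against.** Section 7.2 also words the primary endpoint as a change, then defines a responder by a 50% cut. Change in RBANS may be the same shorthand for the 20% rule in sections 2 and 3.4. That is possible, but item 8 carries no threshold, and on that reading the 20% proportion is the endpoint: the low-power form, with no test named for it.

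Item 8 sits among predictors, so it may not be meant as a between-arm outcome at all. It may equally be the cognitive aim run on to the list. Section 3.2 treats cognition as a separate second part of the secondary aim ("Secondly, we will assess for improvements in cognitive performance as measured by the KOKMEN", together with RBANS). The placement alone does not show a plan to use RBANS change as a predictor.

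The sentence on continuous outcomes does not name RBANS. This stands: the comparison of ANCOVA with the change score applies only if the change score is tested.

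A change-score test in a randomised trial is valid and unbiased. This also stands. A reader might infer that the planned test is wrong, or that ANCOVA always wins; neither is supported. The issue is efficiency, and the advantage disappears at high correlation (step 3).

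A reader might also infer that the comparison could be made at any visit. The schedule leaves only week 6, so the missing time point is a matter of wording.

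**Conclusion.** The point holds as an improvement to a secondary analysis. The cognitive endpoint has two forms, the plan does not choose between them for the between-arm comparison, and neither adjusts for a baseline score that both arms already provide.

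If the change score is tested, adjustment gains about 11 / 5 / 2 percentage points of power at correlations of 0.5 / 0.7 / 0.8. If the 20% proportion is tested, the loss is far larger: at a correlation of 0.7 and a 12-point effect, about 24% power against 83% for ANCOVA.

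These sizes rest on an assumed SD, correlation, effect and, for the 20% cut, baseline mean and placebo change. They are illustrations, not estimates for this trial. The primary endpoint and its stated 89% power are unaffected.

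**What to change.** - **Section 7.1:** make the between-arm cognitive analysis the week-6 RBANS score by ANCOVA, with treatment and baseline RBANS as terms. Report the adjusted difference with its 95% CI. Name the score, for example the total scale.
- **Supportive analysis:** keep the 20% proportion at week 6, stating that it is relative to the patient's own baseline and compared by Fisher's exact test.
- **Sections 2, 3.4 and 7.2:** state the same score, form and time point in each. In 7.2, list RBANS as the cognitive endpoint rather than as item 8 of the predictors.

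The cost is one degree of freedom and SAP wording. No new data or visits are needed, the 20% proportion is kept, and the primary analysis does not change. The wording should be fixed before the first week-6 unblinding or, if that has passed, before any comparison of RBANS by arm.
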